4. SUBJECT DISPOSITION

4.1. Subject Enrollment and Disposition

A summary of subject enrollment will be provided by treatment group for each country, Investigator within a country, and overall. The summary will present the number and percentage of subjects randomized. For each column, the denominator for the percentage calculation will be the total number of subjects analyzed for that column.

A similar enrollment table will be provided by randomization stratum. The denominator for the percentage of subjects in the stratum will be the total number of randomized subjects. If there are discrepancies in the value used for stratification assignment between the IRT and the clinical database, the value collected in the clinical database will be used for the summary. A listing of subjects with discrepancies in the value used for stratification assignment between the IRT and the clinical database at the time of data finalization will be provided. The randomization schedule used for the study will be provided as an appendix to the CSR.

A summary of subject disposition will be provided by treatment group. This summary will present the number of subjects randomized, and the number of subjects in each of the categories listed:

- Full Analysis Set
- Safety Analysis Set

The number and percentage of the subjects in the following categories will be summarized using the Safety Analysis Set:

- Completed ABI-H2158/PBO
- Did not complete ABI-H2158/PBO and reasons for study drug discontinuation
- Completed ETV
- Did not complete ETV and reasons for study drug discontinuation
- Completed study
- Did not complete the study and reasons for study discontinuation

For the status of study drug and study completion and reasons for premature discontinuation, the number and percentage of subjects in each category will be provided. The denominator for the percentage calculation will be the total number of subjects in the Safety Analysis Set corresponding to that column.

4.2. Extent of Study Drug Exposure

Extent of exposure to ABI-H2158/PBO and to ETV will be examined by assessing the total duration of exposure to each drug.

4.2.1. Duration of Exposure to Study Drug

Total duration of exposure to a drug will be defined as last dose date minus first dose date plus 1, regardless of any temporary interruptions in drug administration, and will be expressed in weeks using up to 1 decimal place (eg, 4.5 weeks). Duration (weeks) = Duration (days) /7. If the last dose date is missing, the latest date among the drug end date, clinical visit date, laboratory sample collection date, and vital signs assessment date that occurred during the on-treatment period will be used for subjects included in the final analyses or the last available date in the database snapshot for subjects who were still on treatment at the time of an interim analysis.

The total duration of exposure to ABI-H2158/PBO and to ETV will be summarized using descriptive statistics. Summaries will be provided by treatment group for the Safety Analysis Set. The expected total duration of on-treatment therapy for all subjects is 72 weeks. The distribution of subjects by the total number of weeks on therapy (ie, <12 weeks, 12 -<24 weeks, 24 -<48 weeks, ≥48 weeks) will be presented. The cumulative distribution of subjects will also be presented using the following cutoffs: at least 1 dose, ≥2 weeks, ≥4 weeks, ≥8 weeks, ≥12 weeks, ≥24 weeks, ≥36 weeks, ≥48 weeks, and ≥72 weeks.

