1.2. Study Design

This study will assess the safety, antiviral activity, and pharmacokinetics (PK) of ABI-H2158 administered once daily (QD) in combination with ETV in subjects with cHBV. Multiple parallel cohorts will be enrolled in the study.

In Cohort 1, approximately 40 treatment-naïve subjects with HBeAg positive cHBV will be randomized in a 3:1 ratio to receive 300 mg ABI-H2158+ETV (n=30) or matching PBO+ETV (n=10) for 72 weeks (Figure 1-1). In Cohort 2, approximately 40 treatment-naïve subjects with HBeAg negative cHBV will be randomized in a 3:1 ratio to receive 300 mg ABI-H2158+ETV (n=30) or matching PBO+ETV (n=10) for 72 weeks (Figure 1-1). Treatment assignments for Cohort 1 will be stratified by the HBV DNA level measured at the Screening visit (ie, $\geq 8.0 \log_{10}$ IU/mL versus $< 8.0 \log_{10}$ IU/mL) and for Cohort 2 will be stratified by the HBV DNA level measured at the Screening visit (ie, $\geq 6.0 \log_{10}$ IU/mL versus $< 6.0 \log_{10}$ IU/mL).

After completing treatment at Week 72, or following premature treatment discontinuation, all subjects will enter a 24 week follow-up period. During the follow-up period all subjects will remain on ETV and undergo the follow-up assessments. After completing the 24-week follow-up period, all subjects will resume management by their treating physician in accordance with local standard of care.

[figure not shown]
The schedule of assessments is presented in Protocol Appendix 1.

An assessment of PK data will also be performed after all subjects have completed study Week 4 (or discontinued study without completing Week 4) in order to confirm the absence of important drug interactions between ABI-H2158 and ETV at steady state.

Following the early termination of Study ABI-H2158-201, in accordance with the ABI-H2158-201 Protocol Clarification Letter for Amendment 2 dated 14 Dec 2020, 07 September 2021, subjects were instructed to complete the follow-up assessments through 12 weeks after the last dose of study medication.

Throughout the 12-week follow-up period, all subjects should continue treatment with ETV.

Figure 1-1. Study Overview

Abbreviations: PBO: placebo; ETV: entecavir; HBeAg: hepatitis B “e” antigen.

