3.6. Analysis Visit Windows

3.6.1. Definition of Study Day

In this study, study drug is defined as ABI-H2158 (or matching PBO) and ETV.

The first dose date of ABI-H2158/PBO and of ETV will be calculated. Study Day 1 is defined as the first dose date of study drug, which is the minimum of the first dose dates of ABI-H2158/PBO and ETV in a treatment group. If the first dose date is missing, the date of randomization will be used.

The last dose date of ABI-H2158/PBO and of ETV will be calculated. The last dose date for each drug will be the end date on the respective “Subject Disposition: End of the Treatment” eCRF. The last dose date of study drug will be defined as the maximum of the last dose dates of ABI-H2158/PBO and ETV in a treatment group.

Study day will be calculated from Study Day 1 and derived as follows:

- For days prior to the first dose: Assessment Date – Study Day 1
- For postdose study days: Assessment Date – Study Day 1 + 1

For the follow-up period, the follow-up Study Day 1 is defined as the day after the last dose date of ABI-H2158/PBO and the follow-up study day will be calculated from the last dose date and derived as Assessment Date – Last Dose Date of ABI-H2158/PBO.

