3.6.2. Analysis Visit Windows

Subject visits might not occur on protocol-specified days. Therefore, for the purpose of analysis, observations will be assigned to analysis windows. In general, the baseline value will be the last nonmissing value on or prior to the first dose date of study drug. The “on-treatment” period is defined up to the last dose date of ABI-H2158/PBO. The “off-treatment” period is defined after the last dose of ABI-H2158/PBO through the follow up period.

The assessment schedule is different in the Korea country specific protocol amendment. The analysis window will follow what is specified in the global protocol.

The analysis windows for on-treatment study assessments, including HBV DNA, HBV pgRNA, HBsAg, HBeAg, HBcrAg, adverse events, and clinical laboratories (chemistry, hematology, coagulation, urinalysis) are provided in [Table 3-1](#).

Table 3-1. On-Treatment Analysis Visit Windows for Study Assessments

Nominal Visit	On-Treatment Nominal Study Day	Visit Window Study Day	
		Lower Limit	Upper Limit
Day 1	1	(none)	1
Week 2	14	2	21
Week 4	28	22	42
Week 8	56	43	70
Week 12	84	71	98
Week 16	112	99	126
Week 20	140	127	154
Week 24	168	155	182
Week 28	196	183	210
Week 32	224	211	238
Week 36	252	239	266
Week 40	280	267	294
Week 44	308	295	322
Week 48	336	323	350
Week 52	364	351	378
Week 56	392	379	406
Week 60	420	407	434
Week 64	448	435	462
Week 68	476	463	490

Nominal Visit	On-Treatment Nominal Study Day	Visit Window Study Day	
		Lower Limit	Upper Limit
Week 72	504	491	≥504

The analysis windows for electrocardiograms (ECG) measurements are provided in [Table 3-2](#).

Table 3-2. On-Treatment Analysis Visit Windows for ECG

Nominal Visit	On-Treatment Nominal Study Day	Visit Window Study Day	
		Lower Limit	Upper Limit
Day 1	1	(none)	1
Week 12	84	2	126
Week 24	168	127	210
Week 36	252	211	294
Week 48	336	295	378
Week 60	420	379	462
Week 72	504	463	≥504

The analysis windows for off-treatment study assessments, including HBV DNA, HBV pgRNA, HBsAg, HBeAg, HBcrAg, vital signs, concomitant medications and adverse events, chemistry, hematology, coagulation and urinalysis are provided in [Table 3-3](#).

Table 3-3. Off-Treatment Analysis Visit Windows for Study Assessments

Nominal Visit	Off-Treatment Nominal Study Day	Visit Window Study Day	
		Lower Limit	Upper Limit
FU-Week 4	28	1	42
FU-Week 8	56	43	70
FU-Week 12	84	71	≥84

The analysis windows for ECG is provided in [Table 3-4](#).

Table 3-4. Off-Treatment Analysis Visit Windows for ECG

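### SAP 4.2.1 uses one rule for a missing last dose date of either drug: on its natural reading it can cut ETV exposure at the ABI-H2158/PBO stop, and it gives no usable bound for ABI-H2158/PBO

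*Combined protocol and SAP*

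**What the plan says.** SAP 4.2 treats the two drugs separately: "Extent of exposure to ABI-H2158/PBO and to ETV will be examined by assessing the total duration of exposure to each drug". SAP 4.2.1 gives the measure: "Total duration of exposure to a drug will be defined as last dose date minus first dose date plus 1". Under SAP 3.6.1 the date normally comes from a form for each drug: "The last dose date for each drug will be the end date on the respective" End of the Treatment eCRF.

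If that date is missing, SAP 4.2.1 has a single rule for both drugs. It takes the latest among the drug end date, the clinic visit date, the laboratory collection date "and vital signs assessment date that occurred during the on-treatment period will be used for subjects included in the final analyses". SAP 3.5.1 points to this section, and to no other, for a missing last dose date.

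The period named in the rule is defined once, in SAP 3.6.2, by one drug only. The on-treatment "period is defined up to the last dose date of ABI-H2158/PBO", and the off-treatment "period is defined after the last dose of ABI-H2158/PBO through the follow up period". Meanwhile ETV continues. SAP 1.2 says of the situation after early termination: "Throughout the 12-week follow-up period, all subjects should continue treatment with ETV".

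SAP 3.6.1 then combines the two drugs: "The last dose date of study drug will be defined as the maximum of the last dose dates of ABI-H2158/PBO and ETV".

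**The concern.** The two drugs stop at different times, but one rule bounded by one drug's stop serves both.

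- **ETV.** Dates in follow-up are the evidence that ETV was still being taken, and the rule appears to bar them. ETV exposure would be cut short for subjects with a blank ETV date and tabulated beside subjects with a recorded date, whose follow-up exposure counts in full.
- **Concomitant medications.** SAP 7.4.2 leaves out a medicine started after the last dose of study drug. If a blank ETV date pulls that date back, the same medicine could count for one subject and not for another with the same history.
- **ABI-H2158/PBO.** The rule selects dates from a period whose end is the date to be found. That date also sets the on/off-treatment split (SAP 3.6.2), the adverse event windows (SAP 7.1.5 and 7.1.6) and the laboratory windows (SAP 7.2.1). Development stopped because of ALT elevations (SAP 1), so these windows should not rest on a programmer's choice.

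**Working it through.** **1. The plan's own figure.** Exposure in weeks = (last dose day − first dose day + 1)/7. With first dose on Day 1 and nominal Week 72 on Day 504 (SAP Table 3-1), this gives (504 − 1 + 1)/7 = 72.0 weeks. It agrees with the expected on-treatment duration in SAP 4.2.1.

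**2. Missing ETV date, natural reading.** Inputs: follow-up of 12 weeks = 84 days (SAP 1.2), ETV taken throughout it, and the latest qualifying date falling on the last ABI-H2158/PBO dose. The stop weeks are assumptions; the documents give none.

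| Assumed ABI-H2158/PBO stop | Actual ETV weeks | ETV weeks under the rule | Loss | Four-band exposure category |
|---|---|---|---|---|
| Week 4 (Day 28) | (28+84)/7 = 16.0 | 4.0 | 12/16 = 75% | 12 to <24 becomes <12 |
| Week 12 (Day 84) | (84+84)/7 = 24.0 | 12.0 | 12/24 = 50% | 24 to <48 becomes 12 to <24 |
| Week 24 (Day 168) | (168+84)/7 = 36.0 | 24.0 | 12/36 = 33% | unchanged |
| Week 36 (Day 252) | (252+84)/7 = 48.0 | 36.0 | 12/48 = 25% | ≥48 becomes 24 to <48 |
| Week 48 (Day 336) | (336+84)/7 = 60.0 | 48.0 | 12/60 = 20% | unchanged |

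The Week 24 case keeps its band but drops out of the cumulative ≥36-week row. If the last qualifying date falls before the last ABI-H2158/PBO dose, that gap adds to the loss. If ETV stopped during follow-up, the loss is smaller.

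**3. Concomitant medications.** Take the Week 24 case and a medicine started six weeks into follow-up, on Day 168 + 42 = 210. With a recorded ETV end on Day 252, the last dose date of study drug is max(168, 252) = 252, and the medicine counts. With a blank ETV date the imputed value is at most Day 168, the maximum is 168, and the medicine is left out because 210 > 168.

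**4. Missing ABI-H2158/PBO date, natural reading.** The upper bound of the search is the last ABI-H2158/PBO dose, which is the unknown. The definitions alone give no value. By contrast, SAP 3.6.1 has a workable fallback for a missing first dose date (the randomization date).

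**5. Narrower reading.** Suppose the on-treatment qualifier attaches only to the vital signs date. Follow-up visit and laboratory dates then qualify for both drugs, and the ETV loss in step 2 disappears. But with ABI-H2158/PBO stopped on Day 168 and a last follow-up visit on Day 252, a missing ABI-H2158/PBO date is imputed as 252/7 = 36.0 weeks instead of 24.0, which is 12 weeks too long. Carried into the 28-day safety window, the window would end on Day 252 + 28 = 280 instead of Day 168 + 28 = 196.

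**The case against.** The strongest reply is that the rule may never be used. Each drug has its own end-of-treatment form. SAP 4.1 tabulates ETV completion and reasons for non-completion. SAP 2.2 holds the final analysis until queries are settled, and protocol 7.5 requires ETV accountability at follow-up visits, so a query could recover a blank date. This stands as a limit on reach: the number of affected subjects could be zero. It does not make the rule right when it is used.

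Second, the qualifier may belong to the last listed item only. That reading is possible, but it moves the error to ABI-H2158/PBO, as step 5 shows.

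Third, an exposure summary with an expected 72 weeks and a top cutoff of ≥72 weeks may be meant to describe the treatment period alone. The documents do not settle this. But SAP 3.6.1 accepts a recorded ETV end date wherever it falls, so recorded and imputed subjects would still be measured on different scales.

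Fourth, the drug end date in the list may be a separate eCRF field, which would supply an ABI-H2158/PBO date in practice. The eCRF is not available to check. If so, the circularity matters less, but an ETV end date in follow-up would still fall outside the on-treatment period.

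Fifth, the ETV limb does not touch the adverse event or laboratory windows, which use the ABI-H2158/PBO date, and every medication is still listed by subject. Both points are correct.

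**Conclusion.** The point holds as a flaw in a stated rule, of minor weight. One imputation rule cannot serve two drugs with different stop dates, and it fails on either reading. For a subject with a missing ETV date who stayed on ETV in follow-up, the natural reading loses up to about 12 weeks of ETV exposure. For a missing ABI-H2158/PBO date it gives either no defined bound or, on the narrower reading, up to about 12 weeks too much. The effect is confined to subjects with missing dates. It falls mainly on descriptive exposure and concomitant-medication tables, and reaches the safety windows only if the ABI-H2158/PBO date is missing.

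A reader might infer more, and the documents do not support it:

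- That ETV end dates are the ones most likely to be blank. Nothing in the documents says so.
- That every affected subject loses 84 days. Protocol 7.9.1 leaves ETV to the Investigator's discretion after some discontinuations.
- That the loss should be put at 24 of 96 weeks, from the planned 72 weeks of treatment and 24 of follow-up. This SAP was written after termination and analyses a 12-week follow-up.
- That the primary efficacy model is wrong. It is not the target, although the on-treatment period also uses the ABI-H2158/PBO date.

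**What to change.** Replace the single rule in SAP 4.2.1 with one rule per drug.

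- **ETV:** use the latest ETV accountability date or, failing that, the latest visit or laboratory date through the end of study participation, unless ETV discontinuation is recorded. Flag imputed dates in the listing.
- **ABI-H2158/PBO:** use recorded dispensing and return (accountability) dates or study drug administration dates, capped at the Premature Termination or end-of-treatment visit date. Make no reference to the on-treatment period.

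The cost is about two SAP sentences and a small change to the exposure program. Accountability is already recorded (SAP 4.2.2; protocol 7.5 and 7.7), so no new data are needed. The downside is small: ETV exposure may be slightly overstated where an ETV stop went unrecorded, and the flag lets a reader see where.

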4.2.2. Study Drug Compliance

The total number of tablets administered and average daily dose will be summarized using descriptive statistics.

The presumed total number of tablets administered to a subject will be determined by the data collected on the drug accountability CRF using the following formula:

$$\begin{aligned} & \text{Total Number of Tablets Administered} \\ &= \left(\sum \text{No. of Tablets Dispensed} \right) - \left(\sum \text{No. of Tablets Returned} \right) \end{aligned}$$

4.2.2.1. On-Treatment Compliance

The level of on-treatment compliance to ABI-H2158/PBO and to ETV will be determined by the total amount of study drug administered relative to the total amount of study drug expected to be administered during a subject's actual on-treatment period.

The level of on-treatment compliance will be expressed as a percentage using the following formula:

$$\text{On-Treatment Compliance (\%)} = \left(\frac{\text{Total Amount of Study Drug Administered}}{\text{Study Drug Expected to be Administered on Treatment}} \right) \times 100$$

Descriptive statistics for the level of on-treatment compliance with the number and percentage of subjects belonging to compliance categories (e.g., < 80%, ≥ 80 to < 90%, ≥ 90%) will be provided by treatment group for the Safety Analysis Set.

The by-subject listings of study drug administration and drug accountability will be provided by subject ID number in ascending order and visit in chronological order.

4.3. Protocol Deviations

Subjects who did not meet the eligibility criteria for study entry but enrolled in the study will be summarized. The number and percentage of subjects who did not meet at least 1 eligibility criterion will be provided for specific criteria by treatment group based on the All Randomized Analysis Set. A by-subject listing will be provided for those subjects who did not meet at least 1 eligibility (inclusion or exclusion) criterion. The listing will present the eligibility criterion (or criteria if more than 1 deviation) that subjects did not meet and related comments, if collected.

Protocol deviations (PDs) occurring after subjects entered the study are documented during routine monitoring. The number and percentage of subjects with important PDs (IPDs) by deviation category will be summarized by treatment group for All Randomized Analysis Set. A by-subject listing will be provided for those subjects with any PDs.

A table will be provided to summarize any COVID-19 related PDs with the deviation reason by treatment group. A table will also be provided to summarize visits that were not performed along with the reason they were not performed. A by-subject listing of subjects who missed visits along with reasons for missed visit will be provided.

5. BASELINE CHARACTERISTICS

5.1. Demographics and Baseline Characteristics

Subject demographic variables (ie, age, age group [$<50/\geq 50$ years], sex, race, and ethnicity), baseline characteristics (body weight, height, body mass index [BMI; in kg/m^2]) will be summarized by treatment group and overall using descriptive statistics for continuous variables and using number and percentage of subjects for categorical variables. The summary of demographic data will be provided for the Safety Analysis Set.

A by-subject demographic listing, including the informed consent date, will be provided by subject ID number in ascending order.

5.2. Baseline Disease Characteristics

Baseline disease characteristics will be summarized by treatment group and overall. Summary descriptive statistics will be used for continuous variables and the number and percentage of subjects will be used for categorical variables. The following factors will be included, but not limited to:

- Years positive for HBV
- HBV Genotype
- Baseline HBV DNA (\log_{10} IU/mL)
- Baseline HBV DNA groups: $\geq 8.0 \log_{10}$ IU/mL and $< 8.0 \log_{10}$ IU/mL for Cohort 1, and $\geq 6.0 \log_{10}$ IU/mL, $< 6.0 \log_{10}$ IU/mL for Cohort 2
- Baseline HBV pgRNA (\log_{10} U/mL)
- Baseline HBeAg (\log_{10} IU/mL)
- HBeAg group ($<$ LLOQ)
- Baseline HBcrAg (\log_{10} kU/mL)
- HBcrAg group ($<$ LLOQ)
- Baseline HBsAg (\log_{10} IU/mL)
- HBsAg group ($<$ LLOQ)
- Baseline HBeAg antibody (HBeAb)

- Baseline HBsAg antibody (HBsAb)
- Baseline antibody to the HBV core-related antigen (HBcrAb)
- Baseline ALT (U/L)
- ALT group (>ULN [Covance], >ULN [AASLD])
- Fibroscan result
- Metavir Fibrosis Stage

A by-subject listing of baseline disease characteristics will be provided by subject ID number in ascending order.

5.3. Medical History

Medical history collected at Screening will be coded using the Medical Dictionary for Regulatory Activities (MedDRA) v23.0. Medical history will be summarized by preferred term (PT), treatment group and overall. Subjects who report 2 or more medical history items that are coded to the same PT will be counted only once by the unique coded term in the summary. The summary will be provided for the Safety Analysis Set.

HBV-specific medical history will be summarized by mode of HBV infection, treatment group and overall. The summary will be provided for the Safety Analysis Set.

A by-subject listing of medical history will be provided by subject ID number in ascending order.

6. EFFICACY ANALYSES

The primary analysis set for efficacy analyses will be the FAS, defined in [Section 3.1.2](#). The efficacy analyses will be performed for the 2 cohorts separately. Nominal p-values will be presented for any treatment comparisons. No multiplicity adjustment will be made.

6.1. Primary Efficacy Endpoint

6.1.1. Definition of the Primary Efficacy Endpoint

The primary efficacy endpoint is the change in mean \log_{10} HBV DNA from Baseline to Week 24 for ABI-H2158+ETV compared to PBO+ETV.

